9.1. APPENDIX A: SUMMARY OF PILOT STUDIES

Based on two previous pilot studies, we selected foods that are palatable for the study population and portion sizes that are perceived as 'normal' in order to limit potential compensatory eating after consuming a meal perceived as being 'smaller than normal'.

In a first pilot study, a selection of seven candidate main meal dishes (3 pasta lunchtime dishes: penne with pesto, spaghetti carbonara, spaghetti Bolognese; 4 dinner dishes: beef curry, chicken korma curry, chilli con carne, sweet and sour chicken [all served with rice]) were photographed on standard-sized (28.5cm diameter) dinner plates at portion sizes ranging from 40 to 300% of a reference portion (equal to the manufacturer's recommended serving for commercially available foods, or equivalent to similar commercially available foods for recipes prepared from ingredients). Participants ($N = 30$, 50% female) completed a computer-based rating task in which they viewed each portion size in a randomised order, and indicated whether they perceived that portion as a 'normal' or 'not normal' amount to eat. The proportion of the sample that perceived each portion size as 'normal' in size to determine the 'norm range' for each dish (i.e., the range of portions perceived as 'normal' by at least 60% of the sample) was calculated. The reduced portion size for each food was selected from the lower end of the norm range, the large portion size from the mid-high end of the norm range.

In a second pilot study, 10 participants (50% female) viewed each main meal dish in the two portion sizes in person. Participants rated the perceived normality of each portion for each dish (grouped by dish, such that they rated the normality of each portion for the first dish, followed by each portion size for the second dish, and so on) on a Likert scale ranging from 1 ("not normal – too small") to 7 ("not normal – too large"), with a midpoint of 4 ("normal"). Participants subsequently tasted each dish and rated how much they liked the taste on a 7-point Likert scale ranging from 1 ("dislike very much") to 7 ("like very much"). All dishes were at least moderately liked by all participants, such that only a small number of participants rated their liking of the meals below the midpoint of the scale ($n = 0$ participants for chilli, $n = 2$ participants for Bolognese, carbonara, pesto, beef curry), and the mean liking rating was above the midpoint of the scale for all dishes (mean ratings for each rice dish was significantly larger than 4, while the mean ratings for each pasta dish was at least 4.5, but did not significantly differ from 4). For most dishes, the mean ratings of the reduced portion sizes did not significantly differ from the midpoint of the scale, and the majority (at least 60%) of participants provided a normality rating of '4' for most dishes indicating that participants perceived these portions as 'normal'. There were two exceptions: the mean normality rating for the reduced portion of pasta with pesto was significantly higher than 4 (indicating perceived 'larger than normal'), and the mean normality rating for the reduced portion of chicken with sweet and sour sauce was significantly lower than 4 (indicating perceived 'smaller than normal'). To ensure that the portions were perceived as *at least* normal in size, sweet and sour chicken with rice was omitted from the menu.

Finally, given logistical considerations (in part relating to running experiments during COVID-19), we decided that each experimental session would last 1 day, meaning only one lunch option and one dinner option would be required. We decided on a final menu based on these pilot studies and logistical considerations, giving 1 lunchtime pasta dish (3-cheese pasta) and 1 dinner dish (chili-con-carne with rice).

9.2. APPENDIX B: BARRATT IMPULSIVENESS SCALE

Instruction: “Read each statement and select the appropriate response. Do not spend too much time on any statement. Answer quickly and honestly.”

		Rarely/Never	Occasionally	Often	Almost always/Always
		1	2	3	4
1.	I “squirm” at plays or lectures.				
2.	I am restless at the theatre or lectures.				
3.	I don’t “pay attention.”				
4.	I concentrate easily.*				
5.	I am a steady thinker.*				
6.	I act “on impulse.”				
7.	I act on the spur of the moment.				
8.	I buy things on impulse.				
9.	I make-up my mind quickly.				
10.	I do things without thinking.				
11.	I spend or charge more than I earn.				
12.	I am happy-go-lucky.				
13.	I am a careful thinker.*				
14.	I plan tasks carefully.*				
15.	I am self-controlled.*				
16.	I plan trips well ahead of time.*				
17.	I plan for job security.*				
18.	I say things without thinking.				
19.	I like to think about complex problems.*				
20.	I like puzzles.*				
21.	I save regularly.*				
22.	I am more interested in the present than the future.				
23.	I get easily bored when solving thought problems.				
24.	I change residences.				
25.	I change jobs.				
26.	I am future oriented.*				
27.	I can only think about one problem at a time.				
28.	I often have extraneous thoughts when thinking.				
29.	I have “racing” thoughts.				
30.	I change hobbies.				

*reverse scoring

9.3. APPENDIX C: SATIETY RESPONSIVENESS

		Strongly disagree 1	Disagree 2	Neither agree nor disagree 3	Agree 4	Strongly agree 5
1.	I often leave food on my plate at the end of a meal.					
2.	I often get full before my meal is finished.					
3.	I get full up easily.					
4.	I cannot eat a meal if I have had a snack just before.					

9.4. APPENDIX D: PLATE CLEARING TENDENCIES

		Strongly disagree 1	Disagree 2	Neither agree nor disagree 3	Agree 4	Strongly agree 5
1.	I always tend to clear my plate when eating.					
2.	I normally finish eating when my plate is empty.					
3.	Before I start eating, I normally plan to finish the serving I am about to eat					
4.	I rarely leave food on my plate					
5.	It is normal for me to have very little food left or an empty plate at the end of a meal					

9.5. APPENDIX E: PERCEIVED FOOD INSECURITY

Instructions: These next questions are about the food eaten in your household in the last 12 months and whether you were able to afford the food you need.

Here are two statements that people have made about their food situation. Please tell me whether the statement was OFTEN, SOMETIMES, or NEVER true for (you/you and the other members of your household) in the last 12 months.

		Often true 1	Sometimes true 2	Never true 3	Don't know DK
Q3	The food that (I/we) bought just didn't last, and (I/we) didn't have money to get more				
Q4	(I/we) couldn't afford to eat balanced meals				

		Yes 1	No 2	Don't know DK
Q8	In the last 12 months, since (date 12 months ago) did (you/you or other adults in your household) ever cut the size of your meals or skip meals because there wasn't enough money for food?			

		Almost every month 1	Some months but not every month 2	Only 1 or 2 months 3	Don't know DK
Q8a	How often did this happen?				

		Yes 1	No 2	Don't know DK
Q9	In the last 12 months, did you ever eat less than you felt you should because there wasn't enough money to buy food?			
Q10	In the last 12 months, were you ever hungry but didn't eat because you couldn't afford enough food?			

NOTES.

If any of the first 3 questions are answered affirmatively (i.e., if either Q3 or Q4 are "often true [1]" or "sometimes true [2]" or Q8 is "yes" [1]), the participant will proceed to Q8a. Otherwise, they will skip to Q9.

All questions are optional (meaning there can be missing data).

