7.2.2. Independent variables

Socioeconomic position (SEP) will be derived from highest educational qualification, coded as lower (1 = No formal qualifications; 2 = 1–3 GCSEs; 3 = 4+ GCSEs; 4 = A level) or higher (5 = Certificate of higher education (CertHE); 6 = Diploma of higher education (DipHE); 7 = Bachelor; 8 = Master’s degree; 9 = Doctorate).

Impulsivity. Items from the Barratt Impulsiveness Scale will be coded from 1 to 4. The higher the summed score for all items, the higher the level of impulsiveness (min. = 30, max. = 120). McDonald’s Omega will be calculated as an indicator of internal consistency.

Inhibition. For correct responses, the median reaction times (RTs) in incongruent and congruent trials will be calculated [53,54]. The difference in median RTs between incongruent vs congruent trials will be calculated [incongruent RT – congruent RT] = *The Stroop interference effect*. Higher scores indicate poorer response inhibition.

Portion size appropriateness. For each participant the average selected portion size will be calculated in kcal.

Satiety responsiveness. Items will be coded from 1: *strongly disagree*, to 5: *strongly agree* and their mean will be calculated. A higher score indicates a higher satiety responsiveness. McDonald’s Omega will be calculated as an indicator of internal consistency.

Plate clearing tendencies. Response options range from 1 to 5: 1 = strongly disagree, to 5 = strongly agree. Responses will be averaged. Higher scores indicate higher plate clearing tendencies. McDonald’s Omega will be calculated as an indicator of internal consistency.

Perceived food insecurity. Based on the recommendations of the authors of the questionnaire [55] responses to the 6 questions about food insecurity will be coded as affirmatives (i.e. “yes”, “often true”, “sometimes true”, “almost every month”, “some months but not every month”) and negatives (i.e. “no”, “never true”, “only 1 or 2 months”). Coding of food security is based on the number of affirmatives as follows: 0-1 = “food secure”, 2-4 = “food insecure without hunger”, 5-6 = “food insecure with hunger”. The responses “don’t know” and blank responses reflect missing data, which will be imputed following best practice guidance [55].

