7.5. Secondary analyses

7.5.1. Mediation analyses

For each participant, we will compute the average daily energy intake in the larger portion condition minus average daily energy intake in the smaller portion size condition, referred below as the portion size effect (PSE).

We will first report and compare the individual measures of impulsivity, inhibition, portion size appropriateness, satiety responsiveness, plate clearing tendencies, perceived food insecurity, resource availability in childhood, food choice motives, and compensatory health beliefs for lower and higher SEP groups using means, standard deviations and T-tests. If we find individual differences for any of these measures between participants of lower and higher SEP, mediation analyses will be performed in order to examine the extent to which it mediates the effect of SEP on the PSE (**Figure 2**).

[figure not shown]

Figure 2. Mediation diagrams for the PSE. Indirect effect of SEP on the PSE through a mediator M = $c - c' = ab$.

The mediation will be tested by estimating the indirect effects of SEP on the PSE through all the potential mediators and testing their indirect effect using bias-corrected bootstrap. We will use the PROCESS macro (Model 4 – one mediator at a time and all together) in SPSS that provides asymmetric bias-corrected bootstrap confidence intervals for inference about the indirect effects using 5,000 bootstrap samples [38]. Mediation will be tested by determining whether or not the confidence intervals of the indirect effects estimates contain zero.

If we do not find evidence that the PSE is moderated by SEP or that our individual difference measures do not explain moderation by SEP, we will repeat the primary analysis replacing SEP with the individual measures, to examine whether any of the individual difference measures moderates the main effect of portion size on daily energy intake.

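### Appendix E routes some participants who answer No to Q8 into its follow-up Q8a, and 7.2.2 scores Q8a with no condition on Q8, so a food-insecurity point that is not a valid Q8 frequency is possible

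*Combined protocol and SAP*

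**What the plan says.** Appendix E (9.5) lists six items: Q3, Q4, Q8, Q8a, Q9 and Q10. Q8 asks whether adults in the household cut or skipped meals for lack of money, with answers Yes, No and Don't know. Q8a follows directly and asks how often this happened. It offers three positive frequencies and Don't know, with no option for never or not applicable.

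The routing note begins "If any of the first 3 questions are answered affirmatively". It spells this out as Q3 or Q4 often or sometimes true, or Q8 yes, and concludes "the participant will proceed to Q8a. Otherwise, they will skip to Q9". It also makes every item optional.

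On scoring, 7.2.2 says that "responses to the 6 questions about food insecurity will be coded as affirmatives" or negatives. For Q8a, the two higher frequencies are affirmative and the lowest (one or two months) is negative. It continues "Coding of food security is based on the number of affirmatives as follows": 0-1 is food secure, 2-4 food insecure without hunger, and 5-6 food insecure with hunger. Don't know and "blank responses reflect missing data, which will be imputed following best practice guidance". Both the coding and the imputation are attributed to the guide cited as reference 55. The printed text does not link the scoring of Q8a to the answer on Q8.

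On use, 7.5.1 compares the individual-difference measures "for lower and higher SEP groups using means, standard deviations and T-tests", and adds: "If we find individual differences for any of these measures between participants of lower and higher SEP, mediation analyses will be performed".

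**The concern.** Q8a makes sense only for someone who has said Yes to Q8. The note makes Q8 one of three sufficient triggers, so a woman who affirmed Q3 or Q4 and denied Q8 is asked how often something happened. If she picks one of the two higher frequencies, 7.2.2 as printed gives her a point. She may read the question as being about meal cutting, in which case the point is for an event she denied. Or she may read it as being about the hardship in Q3 or Q4, in which case it counts something already scored. Neither is a valid Q8 frequency.

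The skip route has a second, smaller gap. A participant with Q8 = No and neither Q3 nor Q4 affirmed goes to Q9 and leaves Q8a blank. Read literally, 7.2.2 treats that blank as missing and imputes it, rather than scoring it negative.

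What is at stake is the accuracy of one candidate mediator or moderator. Perceived food insecurity enters the t-test between SEP groups and, if the groups differ on it, the mediation analysis. It also enters the moderator analysis that 7.5.1 plans if SEP does not moderate the portion size effect, or if the measures do not explain that moderation.

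**Working it through.** The plan gives no figure to reproduce here. The check enumerates answer patterns under the Appendix E routing and applies the 7.2.2 coding and bands, with each item coded 1 (affirmative) or 0 (negative).

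**Step 1. All patterns under the written routing.** Q3, Q4, Q8, Q9 and Q10 give 2^5 = 32 combinations. Q8a is asked unless Q3 = Q4 = Q8 = 0. That leaves 7 × 4 = 28 combinations with Q8a asked (two outcomes each, 56 patterns) and 1 × 4 = 4 with it skipped. The total is 56 + 4 = 60.

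**Step 2. Patterns with Q8 = No.** Q3, Q4, Q9 and Q10 give 16 combinations. Those with Q3 or Q4 affirmed number 3 × 4 = 12 and are sent to Q8a. The other 4 skip to Q9.

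**Step 3. Effect of an affirmative Q8a in the 12 routed patterns.** The score without Q8a is Q3 + Q4 + Q9 + Q10; the score with it is one higher.

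| Score without Q8a | Patterns | Score with Q8a | Category change |
|---|---|---|---|
| 1 | 2 (Q3 only; Q4 only) | 2 | food secure to food insecure without hunger |
| 2 | 5 | 3 | none |
| 3 | 4 | 4 | none |
| 4 | 1 (Q3, Q4, Q9 and Q10) | 5 | food insecure without hunger to food insecure with hunger |

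The count rises in 12 of 12 patterns and the category changes in 2 + 1 = 3 of 12. With Q8 = No and Q8a negative the maximum is 4, so under the printed rule a participant who denied Q8 reaches the 5-6 band only through the Q8a point. Section 7.2.2 defines the category, while 7.5.1 plans means and t-tests without saying whether the count or the category is used. The reach is therefore 3 of 12 patterns for the category and 12 of 12 for the count.

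**Step 4. Other answers to Q8a.** The lowest frequency scores 0, so the extra point is possible but not automatic. Don't know or a blank is missing under 7.2.2 and goes to imputation, so the printed text does not guarantee a 0.

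**Step 5. The 4 skip patterns.** Their scores from the answered items are 0, 1, 1 and 2. If the blank Q8a were imputed as affirmative, the two patterns scoring 1 (Q9 only; Q10 only) would move to 2 and change category. Whether imputation could do this depends on the guide.

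**Step 6. After the change.** If Q8a is asked only when Q8 = Yes, there are 16 × 2 = 32 patterns with Q8 = Yes and 16 with Q8 = No, 48 in all. The 60 − 48 = 12 contradictory patterns disappear and the score range stays 0-6.

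**The case against.** The strongest reply is that 7.2.2 adopts a published guide for both coding and imputation, so the printed lines may be only a summary. If the guide scores Q8a only after a Yes to Q8, no stray point arises. It may equally tell the analyst to treat a skipped Q8a as negative. This stands as a limit on the scoring consequence. It does not repair the routing note, which still puts a follow-up question to people who denied the event, and it leaves the protection to a rule that the protocol does not print.

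A second reply is that nobody is forced to give a frequency: she can choose the lowest frequency, choose Don't know or leave the item blank. That is right, and a reader might wrongly infer that every routed participant gains a point. Only the lowest frequency is a clear zero, though. A blank is not a clear way out either, because 7.3 says participants will be asked again for missing answers while Appendix E makes items optional.

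Third, one of the three category changes concerns a woman who affirmed Q10, being hungry but not eating. Placing her in the with-hunger category is not evidently a wrong description of her. What can be said is that she gets there through an answer inconsistent with her own Q8.

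Finally, the pattern counts carry no response rates. The shares 3 of 12 and 12 of 12 must not be read as the proportion of participants misclassified.

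**Conclusion.** The point holds as a minor one. The routing error is plain on the face of Appendix E. The scoring consequence follows from the printed text of 7.2.2, but with less certainty, because the cited guide was not available and may resolve it.

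Three stronger readings are not supported:

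- **Bias in the SEP comparison.** The documents give no response frequencies by education group, so neither the number affected nor the direction can be stated.
- **Effect on the main result.** The primary ANOVA on daily energy intake does not use this measure.
- **Fallback moderator because the groups do not differ on food insecurity.** Section 7.5.1 ties that analysis to SEP not moderating the portion size effect, or to the measures not explaining the moderation.

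The reach is confined to the SEP-group t-test on this measure, the mediation analysis if the groups differ on it, and that moderator analysis. Mediation is judged by whether bootstrap confidence intervals contain zero, so the 0.01 level that section 7 sets for secondary analyses is not the criterion there.

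**What to change.** Change the Appendix E note to: *Q8a is shown only if Q8 = Yes; all others go to Q9.*

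Add to 7.2.2: *If Q8 = No, Q8a is scored negative whatever was entered or left blank.* This sentence also settles the blank Q8a of a participant who answered No to Q8 and was skipped to Q9.

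Recode any data already collected in the same way. Leave Q8 = Don't know or blank to the guide already cited.

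The cost is one skip-logic edit and one sentence. A retrospective recode needs only the stored Q8 and Q8a answers, and no new data.

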9.6. APPENDIX F: PERCEIVED RESOURCE AVAILABILITY IN CHILDHOOD

Instructions: Think about your childhood before age 12 and rate your agreement or disagreement with the following statements.

	Strongly disagree 1						Strongly agree 7
My family had enough money for things growing up.							
I grew up in a relatively wealthy neighbourhood.							
I felt relatively wealthy compared to others my age.							

9.7. APPENDIX G: HEALTH AND WEIGHT CONTROL FOOD CHOICE MOTIVES

Instruction: "Several different factors influence our choice of food. Read each item carefully and decide how important the item is to you. There are no right or wrong answers, we are interested in what is important to you."

It is important to me that the food I eat on a typical day...

		Not at all important 1	A little important 2	Moderately important 3	Very important 4
Health					
1.	contains a lot of vitamins and minerals				
2.	keeps me healthy				
3.	is nutritious				
4.	is high in protein				
5.	is good for my skin/teeth/hair/nails etc.				
6.	is high in fibre and roughage				
Weight control					
7.	is low in calories				
8.	helps me control my weight				
9.	is low in fat				
10.	This is an attention check. Please choose the answer (2) 'A little important'				

9.8. APPENDIX H: COMPENSATORY HEALTH BELIEFS

Instruction: "Different people believe different things regarding their health. Below is a list of beliefs that everyone may hold to some degree. Please read each sentence carefully and rate how closely the idea matches your own belief. Since we all believe different things, there are no correct or incorrect choices. As well, most of these beliefs have not been scientifically tested. How closely does each of the following ideas match your own belief?"

	Not at all 1	A little 2	Somewhat 3	Quite a bit 4	Very much 5
Eating dessert can be made up for by skipping the main dish					
Using artificial sweeteners compensates for extra calories					
Breaking a diet today may be compensated for by starting a new diet tomorrow					

If I eat a small meal, it's fine to have a larger portion during the next meal					
To maintain your weight, it is fine to eat a large meal, if you eat a small portion during the next meal					
To maintain your weight, it is fine to eat a high caloric snack in between meals, if you compensate for this by eating a smaller portion later in the day					
If I eat a small meal, there is no harm in eating more cookies and candies					

9.9. APPENDIX I: INTEROCEPTIVE ACCURACY SCALE

Below are several statements regarding how accurately you can perceive specific bodily sensations. Please rate on the scale how well you believe you can perceive each specific signal. For example, if you often feel you need to urinate and then realise you do not need to when you go to the toilet you would rate your accuracy perceiving this bodily signal as low.

Please only rate how well you can perceive these signals without using external cues, for example, if you can only perceive how fast your heart is beating when you measure it by taking your pulse this would not count as accurate internal perception.

	Strongly disagree	Disagree	Neither agree nor disagree	Agree	Strongly agree
	1	2	3	4	5
1. I can always accurately perceive when my heart is beating fast					
2. I can always accurately perceive when I am hungry					
3. I can always accurately perceive when I am breathing fast					
4. I can always accurately perceive when I am thirsty					
5. I can always accurately perceive when I need to urinate					
6. I can always accurately perceive when I need to defecate					
7. I can always accurately perceive when I encounter different tastes					
8. I can always accurately perceive when I am going to vomit					
9. I can always accurately perceive when I am going to sneeze					
10. I can always accurately perceive when I am going to cough					
11. I can always accurately perceive when I am hot/cold					
12. I can always accurately perceive when I am sexually aroused					
13. I can always accurately perceive when I am going to pass wind					
14. I can always accurately perceive when I am going to burp					
15. I can always accurately perceive when my muscles are tired/sore					
16. I can always accurately perceive when I am going to get a bruise					
17. I can always accurately perceive when I am in pain					
18. I can always accurately perceive when my blood sugar is low					
19. I can always accurately perceive when someone is touching me affectionately rather than non-affectionately					
20. I can always accurately perceive when something is going to be ticklish					
21. I can always accurately perceive when something is going to be itchy					
